### **9.7.2. Final Safety Report**

The feasibility of conducting a final comparative study will be evaluated at an interim time point and at 7-years of follow up based on statistical power and suitable overlap in patient populations in the exposure groups. The feasibility assessment, like the final report, will be conducted using safety events of interest identified through linkages with the patient, cancer and death registers, as appropriate. ARTIS will apply an ICD-code based algorithm to identify serious infections, GI perforations, herpes zoster, and CV events (MACE), in the Swedish patient register. Appendix 4 describes the algorithms used to identify these endpoints in ARTIS and relevant validation references, along with definitions used by other EU registers. The specific algorithms for defining those endpoints have not been validated, though the Swedish patient register has been validated several times (Ludvigsson 2011). The overall positive predictive value (PPV) of the inpatient diagnoses generally ranged from 85% to 95%. A regional validation study of hospitalized acute MI and stroke (components of the MACE endpoint) found positive predictive values of 96% and 94% respectively, in the period 1977 to 1987 (Lindblad, 1993). An ICD-9 code based algorithm applied to inpatient diagnoses of GI perforations in the US demonstrated high PPV (89.1-100) (Curtis, 2011). While the ICD algorithms used by ARTIS to define the endpoints of interest may not be validated, their use can be justified given the importance to contextualize the study results with historical findings. ARTIS has previously conducted and published studies of serious infections (Askling, 2007), PML (Arkema, 2012), and MACE (Michaud, 2016) events in RA patients.

The Swedish national register for contagious diseases, will serve as source of information on TB and other possibly serious contagious diseases for which there is a mandatory registration in Sweden. These reports will be based on a standardized analytical scheme, with some but limited flexibility to add additional endpoints and stratification, and will contain populated tables in line with the shells in Appendix 2. Whether these reports include formal comparisons of patients exposed to tofacitinib and bDMARDs will be determined a priori based on adequate power.

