**Appendix 4. ICD and MedDRA Codes For Select Safety Endpoints**

Event	ARTIS		BIOBADASER, BSRBR, RABBIT
	Operationalization	Validation ICD	Operationalization (Final list TBD based on reported endpoints).
Serious infections	Hospitalizations in the Patient Register listing as main diagnosis ICD10-codes below. If main diagnosis is RA, contributory diagnoses are also considered. A00-B99 (excluding A33 and A50), D73.3, E32.1, G00-G02, G04.2, G05-G07, H00.0, H44.0, H60.0-H60.3, H66-H67, H70, I30.1, I40.0, J00-J22, J32, J34.0, J36, J39.0-J39.1, J44.0, J85, J86, K04.4, K04.6, K04.7, K10.2, K11.3, K12.2, K14.0, K57.0, K57.2, K57.4, K57.8, K61, K63.0, K65.0, K65.1, K65.2, K65.9, L00-L08, L30.3, M00-M01, M46.2-M46.5, M60.0, M65.0, M71.0, M71.1, M72.6, M86, N13.6, N15.1, N15.9, N30.0 N30.8, N34.0, N41.2, N43.1, N45.2, N45.3, N45.4, N48.2, N61, N70, N73, N75.1	This algorithm has not been specifically validated in ARTIS, but the register itself is subject to strict quality assurance routines and has been validated several times. Refs: Ludvigsson et al. External Review and Validation of the Swedish National Inpatient Register, BMC Public Health, 2011 (11):450. http://www.socialstyrelsen.se/register/halsodataregister/patientregistret/inenglish .	Hospitalization and/or use of parenteral antibiotics+ MedDRA Infections and Infestations SOC 10021881.
HZ reactivation	Hospitalizations in the Patient Register listing as main diagnosis ICD10-codes B00 and B02. If main diagnosis is RA, contributory diagnoses are also considered.	The algorithm used to identify this endpoint in ARTIS has not been validated and is expected to only identify the most severe cases.	10019974 Herpes zoster, 10019983 Herpes zoster ophthalmic, 10030865 Ophthalmic herpes zoster, 10058428 Herpes zoster multi-dermatomal, 10063491 Herpes zoster oticus, 10065038 Herpes zoster disseminated, 10065119 Necrotising herpetic retinopathy, 10072210 Genital herpes zoster, 10074241 Varicella zoster gastritis, 10074245 Herpes zoster pharyngitis, 10074248 Herpes zoster meningoencephalitis, 10074253 Herpes zoster necrotising retinopathy, 10074254 Varicella zoster pneumonia, 10074254 Varicella zoster pneumonia, 10074259 Herpes zoster meningitis, 10074297 Herpes zoster cutaneous disseminated.

090177e199570500\Approved\Approved On: 13-Feb-2022 20:25 (GMT)

090177e199570500\Approved\Approved On: 13-Feb-2022 20:25 (GMT)

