	ARTIS		BIOBADASER, BSRBR, RABBIT
Event	Operationalization	Validation ICD	Operationalization (Final list TBD based on reported endpoints).
CV risk	Major Acute Cardiovascular Events (MACE), combines MI, stroke, and fatal cardiovascular events: I00-I99 as main cause of death, or I20.0, I21, I60-I64 as diagnosis in in- or outpatient care.	
See Serious Infections
 
‘Outcome’ was defined as any first-ever ACS event, which in turn was defined as a primary discharge diagnosis of acute myocardial infarction or unstable angina pectoris, or as acute myocardial infarction being the underlying cause of death. For discharge diagnoses, the date of admission to hospital was considered the event date. This outcome definition has previously been validated in a Swedish early RA cohort, with a positive predictive value of 95%. In addition, a regional validation study of hospitalized acute MI and stroke found positive predictive values of 96% and 94% respectively, in the period 1977 to 1987.
 
Lindblad et al. Validity of register data on acute myocardial infarction and acute stroke. Scandinavian Journal of Public health 1993; 21 (1):3-9.
	
Fatal and non-fatal
 
10000891 Acute myocardial infarction; 10006147 Brain stem infarction; 10006148 Brain stem ischaemia; 10008034 Cerebellar infarction; 10008088 Cerebral artery embolism; 10008120 Cerebral ischaemia; 10008190 Cerebrovascular accident; 10014498 Embolic stroke; 10019005 Haemorrhagic cerebral infarction; 10019016 Haemorrhagic stroke; 10024033 Lateral medullary syndrome; 10028596 Myocardial infarction; 10028602 Myocardial necrosis; 10033697 Papillary muscle infarction; 10043647 Thrombotic stroke; 10049768 Silent myocardial infarction; 10051078 Lacunar infarction; 10055677 Haemorrhagic transformation stroke; 10056237 Migrainous infarction; 10059613 Stroke in evolution; 10060839 Embolic cerebral infarction; 10060840 Ischaemic cerebral infarction; 10061256 Ischaemic stroke; 10062573 Brain stem thrombosis; 10064961 Thalamic infarction; 10066591 Post procedural stroke; 10066592 Post procedural myocardial infarction; 10067167 Cerebellar embolism; 10067347 Thrombotic cerebral infarction; 10067462 Millard-Gubler syndrome; 10068621 Cerebellar ischaemia; 10068644 Brain stem stroke; 10069020 Basal ganglia infarction; 10070671 Cerebral septic infarct; 10070754 Inner ear infarction; 10071043 Basal ganglia stroke; 10071260 Carotid angioplasty; 10073945 Perinatal stroke; 10074422 Brain stem embolism;
 
Fatal only
 
10002886 Aortic aneurysm rupture; 10003173 Arterial rupture; 10003210 Arteriosclerosis; 10003212 Arteriosclerosis moenckeberg-type; 10006145 Brain stem haemorrhage; 10007522 Cardiac asthma; 10007554 Cardiac failure; 10007556 Cardiac failure acute; 10007558 Cardiac failure chronic; 10007559 Cardiac failure congestive; 10007559 Cardiac failure congestive; 10007560 Cardiac failure high output; 10007625 Cardiogenic shock; 10007684 Carotid arterial embolus; 10007686 Carotid artery aneurysm; 10007688 Carotid

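### Appendix 4's MACE codes are wider than its MACE definition (non-fatal unstable angina; outpatient codes with no main-diagnosis or incident-event rule), and the PPVs beside them describe narrower inpatient outcomes

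*Protocol*

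**What the plan says.** The CV risk row of Appendix 4 states the concept and the codes in one sentence. The concept "combines MI, stroke, and fatal cardiovascular events". The codes are "I00-I99 as main cause of death, or I20.0, I21, I60-I64 as diagnosis in in- or outpatient care".

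The validation column of the same row cites two sources. The first concerns first-ever acute coronary syndrome, defined as a "primary discharge diagnosis of acute myocardial infarction or unstable angina pectoris, or as acute myocardial infarction being the underlying cause of death"; its stated PPV is 95%. For the second, "a regional validation study of hospitalized acute MI and stroke found positive predictive values of 96% and 94% respectively".

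Other rows of Appendix 4 are tighter. For serious infections the rule is "Hospitalizations in the Patient Register listing as main diagnosis ICD10-codes below", and the herpes zoster row has the same form.

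Section 9.7.2 points to Appendix 4 for the endpoint algorithms used in ARTIS, says that these algorithms have not themselves been validated, and assigns a harmonised ICD algorithm for CV events to the final SAP. Section 9.3.1 lists previous MI among the baseline CV risk factors. Section 9.7.2 stratifies MI and MACE rates by the presence of at least one such factor.

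**The concern.** Estimating event rates is the study's main objective, and MACE was added as an endpoint after the June 2021 signal procedure. A code list wider than the stated endpoint affects the reported rate directly, whether or not a comparative analysis is ever judged feasible.

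Two routes widen it. Non-fatal unstable angina is counted although the definition does not include it. In addition, outpatient codes are accepted without a rule that separates a new event from the follow-up of an old one. Patients with a prior MI or stroke stay in the cohorts, so such visits can occur early in follow-up. Follow-up for an outcome runs until that outcome, so a miscounted visit would also end it and hide any later true event.

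The PPVs of 94% to 96% printed beside the algorithm may lead a reader to believe that this risk has been measured and is small.

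**Working it through.** The protocol gives no figure to reproduce, so the check sets its parts side by side.

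**1. Definition against codes (Appendix 4, CV risk row).**

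| Code element | MI, stroke or fatal CV event? | Within a cited validation? |
|---|---|---|
| I21, inpatient main diagnosis | Yes (MI) | Yes, both studies |
| I60-I64, inpatient | Yes (stroke) | Yes, the regional study (94%) |
| I20.0, non-fatal | No | Yes, the ACS study, as a primary discharge diagnosis |
| I20.0, I21, I60-I64, outpatient | Depends on whether the event is new | No |
| I00-I99 as main cause of death | Yes, as worded | Only where the death is from acute MI |

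I20.0 is the one element that fails the definition outright. The other registers' list in the same row, both its fatal/non-fatal part and its fatal-only part, contains no unstable angina term and no pulmonary embolism term. That list is marked as not final.

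**2. Is there a rule that removes old events?**
- Section 9.2.2 excludes only patients who fail the inclusion criteria. Prior MI or stroke is not an exclusion.
- Section 9.3.1 records previous MI as a baseline factor.
- Section 9.3.2 follows patients until each outcome and states no washout or first-event rule.
- Section 9.4.3 says the Patient Register covers non-primary outpatient visits, so specialist follow-up visits are in the data.
- The cited ACS validation was limited to first-ever events. The algorithm beside it carries no such limit.

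Followed as written, an outpatient contact after index that still carries I21 or an I60-I64 code for an earlier event qualifies.

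**3. Where would such events fall?** Previous MI is itself a CV risk factor in Section 9.3.1, so a patient with a recorded earlier MI is always in the stratum with at least one factor. Recoded old MIs therefore raise the rate in that stratum and exaggerate the contrast with the other. Prior stroke is not on the list. Recoded strokes reach that stratum only through another factor, such as age 65 or over, or hypertension.

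**4. Illustration for the rate.** Let f be the share of counted events that are not new MI, stroke or CV death. Ignoring the small change in person-time, counted rate / true rate = 1 / (1 − f). The document gives no value of f; 10% to 40% is assumed.
- f = 0.10: 1 / 0.90 = 1.11
- f = 0.20: 1 / 0.80 = 1.25
- f = 0.40: 1 / 0.60 = 1.67

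These values show the scale of the possible over-count. They do not estimate it.

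**The case against.** The strongest reply is that the protocol has dealt with this. Section 9.7.2 openly says the algorithms are not validated, justifies them by continuity with earlier ARTIS findings, and leaves a harmonised CV algorithm to the final SAP. Appendix 2 says outcome details will be agreed before each report. This limits the point but does not remove it. Section 9.7.2 names Appendix 4 as the source of the algorithms, and interim reports are scheduled for March 2023 and March 2025. Disclosing that an algorithm is not validated also does not reconcile its codes with its own definition, or make PPVs for other definitions apply to it.

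Other replies stand in part. "Any position" is not stated; it is what the missing restriction allows. Nor does the appendix have a general main-diagnosis rule for MACE to break: the GI perforation and PML rows give no position, and fractures use outpatient data too. Adjusting for history of MI (Appendix 2, models HRb to HRd) and reporting MI separately give partial protection, but neither corrects a miscounted MACE.

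A reader might infer more than the document supports:
- *That I20.0 contradicts the cited validation.* It does not. The ACS outcome explicitly includes unstable angina as a primary discharge diagnosis.
- *That fatal pulmonary embolism contradicts the definition.* It does not. It fits the words for the fatal component, and Section 9.3.3 lists DVT/PE under CV events. Overlap between endpoints is also normal here, since MI is both its own endpoint and part of MACE.
- *That the 6/1000 PY planning rate in Section 9.5 refers to a different endpoint.* That rate is attributed to internal data with no code list, so nobody can say.
- *That the HR is pulled toward 1.* If a share f of comparator events were unaffected by treatment and arose at the same rate in both cohorts, the observed HR would be HR × (1 − f) + f. At f = 0.20, a true HR of 2.0 would appear as 2.0 × 0.80 + 0.20 = 1.8. Nothing in the document supports those conditions. Section 9.9 expects channelling of higher-risk patients to tofacitinib, so recoded old events could be more frequent there and push the HR up.

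**Conclusion.** The point holds in a limited form. The MACE code list departs from its definition through non-fatal I20.0. It also admits outpatient codes without a main-diagnosis or incident-event rule, so old events can be counted as new. The PPVs beside it apply to primary-discharge or hospitalised diagnoses. These conclusions rest on the text alone and on the standard meaning of the ICD-10 codes.

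The size is not known. The share of off-target events is not in the document, and neither the size nor the direction of any effect on the HR can be derived from it. The expected upward shift in the MACE rate, greatest in the risk-factor stratum, assumes that outpatient visits for old events do carry acute codes; the document neither confirms nor excludes this. The correction is worth making before the next report because the endpoint is reported as a rate and the change is cheap.

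**What to change.** In Appendix 4:
1. For primary MACE, take the non-fatal component from inpatient main diagnoses of I21 or I60-I64.
2. Report I20.0 under the broader CV events.
3. Keep the current wide definition as a sensitivity analysis, so that continuity with earlier ARTIS work is preserved and the effect of the wider codes becomes visible.
4. Label the 94% to 96% PPVs as belonging to narrower inpatient definitions.
5. State that venous deaths (I26, I80-I82) count under both MACE and VTE, or report MACE with and without them.

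The cost is an appendix edit and one extra run. The downside is somewhat fewer MACE events in the primary definition, and so a little less precision.
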